1.2.3. Clinical Trials of GS-5829

Study GS-US-350-1604, a Phase 1b/2 study to evaluate the safety, tolerability, PK and pharmacodynamics of GS-5829 as a single agent and in combination with enzalutamide in subjects with CRPC, initiated in November 2015 and is actively enrolling.

1.2.4. Information on Exemestane

Exemestane is an irreversible, steroidal aromatase inactivator, structurally related to the natural substrate androstenedione. It acts as a false substrate for the aromatase enzyme and is processed to an intermediate that binds irreversibly to the active site of the enzyme, causing its inactivation, an effect also known as “suicide inhibition.” Exemestane significantly lowers circulating estrogen concentrations in postmenopausal women. In the US, exemestane is approved for the treatment of advanced breast cancer in postmenopausal women whose disease has progressed following tamoxifen therapy. For current information about exemestane (Aromasin[®]) refer to the prescribing information ([Appendix 9](#)) or the summary of product characteristics in the pharmacy binder.

1.2.5. Information on Fulvestrant

Fulvestrant is an estrogen receptor antagonist that binds to the estrogen receptor in a competitive manner with affinity comparable to that of estradiol and downregulates the ER protein in human breast cancer cells. In vitro studies demonstrated that fulvestrant is a reversible inhibitor of the growth of tamoxifen resistant as well as estrogen sensitive human breast cancer cell lines. In vivo tumor studies fulvestrant delayed the establishment of tumors from xenografts of human breast cancer MCF-7 cells in nude mice. Fulvestrant inhibited the growth of established MCF7 xenografts and of tamoxifen resistant breast tumor xenografts. In the US, fulvestrant is approved for the treatment of hormone receptor positive metastatic breast cancer in postmenopausal women with disease progression following antiestrogen therapy. For current information about fulvestrant (Faslodex[®]), refer to the prescribing information ([Appendix 10](#)) or the summary of product characteristics in the pharmacy binder

1.3. Rationale for Development of GS-5829 in Advanced Solid Tumors and Lymphomas (Group 1)

In 2014, it is estimated that over 500,000 people will die from cancer in the United States (US) alone, with the vast majority due to progression of advanced stage solid tumors {[National Cancer Institute 2014](#)}. Strong evidence exists that the *MYC* oncogene family plays a critical role in the pathogenesis of many of these cancers. Overexpression or amplification of *MYC* has been observed in prostate, breast, colorectal, gastric, melanoma, non-small cell lung, small cell lung, medullary thyroid cancer, rhabdomyosarcoma, multiple myeloma, and aggressive non-Hodgkin's lymphomas such as Burkett's and DLBCL {[He et al 2014](#), [Koh et al 2010](#), [Lin et al 2010](#), [Molyneux et al 2012](#), [Nair et al 2014](#), [Nesbit et al 1999](#), [Odia et al 2013](#), [Petrich et al 2014](#), [van Dam et al 1994](#), [Yoo et al 2004](#)}. GS-5829 is expected to have broad activity in tumors that overexpress *MYC* by decreasing the transcription of *MYC* RNA. GS-5829 also has potential for activity in tumor types that are highly dependent on the activity of other oncogenic transcription factors regulated by BET proteins. These include the AR in prostate cancer {[Asangani et al 2014](#)}, the estrogen receptor and Twist in breast cancer {[Feng et al 2014](#), [Shi et al 2014b](#)}, FOS-like antigen 1 in nonsmall cell lung cancer and pancreatic cancer {[Lockwood et al 2012](#), [Sahai et al 2014](#)}, and Smoothed in basal cell carcinoma and medulloblastoma {[Tang et al 2014](#)}.

In 2014, it is estimated that there will be 233,000 new cases of prostate cancer and 29,480 deaths due to prostate cancer in the US {[National Cancer Institute 2014](#)}. The majority of men (approximately 90%) are diagnosed with loco-regional disease that is treated surgically and/or with radiation therapy; 5-year survival approaches 100% for these patients. However, despite the availability of a variety of therapies, including pharmacological inhibitors of AR activity, immunotherapy, radiation, and chemotherapy, metastatic prostate cancer has a 5-year survival of only 30%, with most patients dying from prostate cancer.

In patients with advanced prostate cancer who have progressed while receiving therapy with chemical or surgical castration, the androgen/AR axis remains the target of current standard of care agents abiraterone and enzalutamide. Primary and acquired resistance to such agents occurs when the AR is activated in an androgen-independent manner, most notably through the expression of the constitutively active AR splice variant 7 (AR-V7) {[Antonarakis et al 2014](#), [Guo et al 2009](#)}. In nonclinical studies, GS-5829 inhibited growth and induced apoptosis in

prostate cancer cell lines by inhibiting MYC expression and AR-target gene expression in both AR- and AR-V7-expressing prostate cancer cell lines.

Diffuse large B-cell lymphoma is the most common subtype of non-Hodgkin's lymphoma, accounting for approximately 30% of all lymphoma diagnoses {Morton et al 2006}. Currently, the combination of rituximab, cyclophosphamide, doxorubicin, vincristine, and prednisone (R-CHOP) is considered to be the standard of care for DLBCL. While approximately half of patients with DLBCL achieve durable remissions, patients who relapse or who are refractory to primary therapy have a poorer outcome. For patients who are not transplant eligible, salvage therapies, which generally include chemotherapy with or without rituximab, offer little chance of prolonged disease control. Response rates range from 30% to 60%, with overall survival less than 12 months {Vacirca et al 2014}.

GS-5829 is being developed for the treatment of DLBCL based on the known role of BET proteins to regulate the transcription of key oncogenic pathways related to MYC, B-cell lymphoma 6 (BCL6), and nuclear factor kappa-light-chain-enhancer of activated B cell (NF- κ B) {Ceribelli et al 2014, Chapuy et al 2013}. In nonclinical studies, GS-5829 reduces the transcription of MYC in DLBCL cell lines *in vitro* and *in vivo*, resulting in potent cell growth inhibition and/or apoptosis. GS-5829 exhibits equivalent potent activity in DLBCL cell lines irrespective of known poor prognosis factors for patients, including activated B-cell (ABC) subclass or MYC/B-cell lymphoma 2 (BCL2) coexpression.

1.3.1. Rationale for Development of GS-5829 in Combination with Exemestane or Fulvestrant for the Treatment of Estrogen Receptor Positive Breast Cancer (Group 2)

[figure not shown]
Approximately 75% of breast cancers express the estrogen receptor (ER), a nuclear hormone receptor and transcription factor that promotes the expression of genes involved in cell growth and survival {Clark et al 1984}. Anti-estrogen endocrine therapies, such as aromatase inhibitors (AIs) and tamoxifen are the primary treatments for early stage ER-positive breast cancers, but many women relapse during or after completing these adjuvant hormonal therapies. In the metastatic setting, single-agent treatment with AIs, tamoxifen, or the selective ER degrader, fulvestrant, has limited benefit. When combined with other targeted therapies such as the Cyclin-Dependent Kinase (CDK) 4/6 inhibitor, palbociclib, the benefit of first-line anti-estrogen therapy significantly improves progression-free survival (PFS). Standard of care includes sequential administration of endocrine therapies until hormone resistance occurs, at which time patients are usually transitioned to chemotherapy and eventually die. Therefore, the development of effective therapies that improve response to endocrine therapy and prevent or reverse resistance continues to be of clinical importance.

Resistance to endocrine therapy is mediated by several mechanisms that enable reactivation of ER-driven transcription under conditions of low estrogen (i.e. estrogen-independent transcription by the ER). These mechanisms include ER overexpression, activating ER mutations, increased expression of ER co-activators, or increased expression of ER-target genes such as MYC and cyclin D1 {Osborne et al 2011}. Importantly, BET proteins are required for both estrogen-dependent and estrogen-independent transcription by the ER receptor. BRD4 and BRD3 are recruited to ER target genes, including MYC, where they promote transcription by

RNA polymerase II. In preclinical studies, the BET inhibitor, JQ1, decreased ER-mediated gene transcription and inhibited the growth of ER-positive tumors {Nagarajan et al 2014, Sengupta et al 2015}. In addition, combination of JQ1 with fulvestrant significantly increased time to disease progression in an endocrine-resistant ER-positive xenograft mouse breast tumor {Feng et al 2014}.

We hypothesize that the combination of GS-5829 and an anti-estrogen such as fulvestrant or an AI such as exemestane, may increase the efficacy of endocrine therapy in patients with advanced ER-positive breast cancer by targeting orthogonal mechanisms (Figure 1-2). The combination is expected to lead to overall greater inhibition of ER-dependent transcription by blocking distinct aspects of ER signaling (reduced ligand-dependent ER activation with AI, reduced ER protein stability with fulvestrant, and reduced BET-dependent transcription of ER target genes with GS-5829). By directly inhibiting the transcription of ER target genes such as MYC, GS-5829 is hypothesized to block established mechanisms of resistance to endocrine therapy. BET proteins also promote transcription of several ER-independent cell cycle genes, including CDK 6, which may additionally contribute to the combination activity in ER+ breast cancer cells. Preliminary Gilead data has demonstrated a synergistic effect of fulvestrant and GS-5829 to inhibit growth of ER-positive cell breast cancer lines in vitro and to inhibit growth of patient-derived ER-positive breast cancer xenografts in mice.

Figure 1-2. Mechanism of Action of GS-5829 to Reduce Transcription of ER Target Genes in Cancer Cells

Overall, the pre-clinical studies demonstrate that GS-5829 is a potent and selective inhibitor of BET proteins and support the use of GS-5829 to treat solid tumors and hematological cancers.

1.3.2. Rationale to Evaluate GS-5829 in Specific Aggressive Non-Hodgkin's Lymphoma: DLBCL and PTCL (Group 3)

Specific subtypes of aggressive lymphoma may have a greater potential for sensitivity to BETi. DLBCL and PTCL are included in this category and are also notable for poor OS for patients in the relapsed and/or refractory setting who are not bone marrow transplant candidates; 9-12 months for relapsed DLBCL {Nagle et al 2013} and 5.5 months for PTCL {Mak et al 2013}. These dismal OS rates highlight an urgent need for improved therapeutic options.

In mature T-cell lymphomas, such as PTCL, BET inhibition may be a favorable target. Cell cycle arrest and reduction of MYC mRNA levels in five out of seven anaplastic large-cell T-cell lymphoma cell lines has been reported with the BETi, OTX-015 {Bonetti et al 2012}.

Data supporting the single agent evaluation of BETi in treating DLBCL have been discussed in Section 1.3.1.

1.3.3. Rationale for the Dose Selection

The starting dose of 0.6 mg GS-5829 was selected based on preclinical repeat-dose toxicology data, where this dose represented 1/6 the highest non-severely toxic dose (HNSTD) in dog, the most sensitive nonclinical species tested. This dose is commensurate with the recommendation outlined in the ICH Guidance for Industry, "S9 Nonclinical Evaluation for Anticancer Pharmaceuticals" (March 2010). The starting dose of 0.6 mg GS-5829 once daily provided margins of approximately 203-fold of the severely toxic dose (STD10) in the mouse (25 mg/kg/day) and 5.5-fold of the HNSTD in the dog (0.1 mg/kg/day) on a human equivalent dose (HED) basis as determined in the repeat dose toxicity studies.

PK data from the first 3 dose levels suggests that exposure in humans is higher than initially predicted and therefore additional intermediate dose levels have been added.

Based on preliminary pharmacokinetic data in the early dose levels of this study, the potentially clinically efficacious exposure (AUC 2.5 h.µg/mL) in humans is anticipated to be achieved with once daily dosing of 3 to 4 mg of GS-5829, which is anticipated to achieve adequate target inhibition for a portion of the dosing interval as supported by in vivo preclinical data.

Dose Levels of 0.6, 1.4, 2.0 and 3.0 enrolled a single subject with the plan to expand to at least 3 subjects if a \geq Grade 2 treatment-related toxicity was observed within the initial dosing period (Study Day 1 through C1D28). No drug related toxicities were observed at Dose Levels 0.6 through 2.0 mg. Should a \geq Grade 2 treatment-related toxicity be observed in the subject receiving 3.0 mg, then a standard 3+3 study design will initiate at the 3.0 mg dose. Should no \geq Grade 2 treatment-related toxicity be observed in the subject receiving 3.0 mg dose, the next dose to be enrolled, Dose Level 4.0 mg will expand enrollment to at least 3 subjects and the study will proceed with a standard 3 + 3 study design. The study will proceed until MTD is identified.

Due to the narrow therapeutic index observed in dogs, the percentage dose increment sequentially decreases at each dose level.

The breast cancer arm of the study (Group 2A and 2B) will initiate at 2.0 mg which has been demonstrated to be safe and tolerable in patients with advanced stage solid tumors and lymphoma in Group 1 of this study. No drug interactions or overlapping toxicities are expected between GS-5829 and exemestane or fulvestrant. Group 2 will not dose escalate beyond the single agent MTD of GS-5829.

The Group 3 lymphoma expansion arm will initiate at a dose \leq to the MTD as determined in Group 1; e.g. a dose that has been demonstrated to be safe and tolerable in patients with advanced stage solid tumors and lymphoma in Group 1 of this study.

1.4. Compliance

This study will be conducted in compliance with this protocol, Good Clinical Practice (GCP), and all applicable regulatory requirements.

every 28 days, until end of treatment followed by a 30-day Safety Follow-Up Visit. Physical examinations will occur on Day 1 of each 28-day cycle until end of treatment, followed by a 30-day Safety Follow-Up visit.

The safety monitoring frequency is considered sufficient to identify potential AEs as they emerge. In addition, mitigation strategies are incorporated into the study design. The inclusion and exclusion criteria are designed to ensure subjects have acceptable organ function to be eligible for this study such that confounding significant co-morbidities are excluded. Study medications will continue until disease progression, unacceptable toxicity, consent withdrawal, or subject's refusal of treatment.

Potential Benefits

The primary potential benefit of BET inhibition is that therapy may delay progression or improve overall survival in patients with lymphoma or solid tumor who do not have alternative therapies which have been demonstrated to provide significant clinical benefit. For patients with breast cancer, the potential benefit of BET inhibition administered in combination with standard anti-estrogen therapy is to delay progression or improve overall survival.

Participants are informed that their involvement in the study may offer benefits to other current or future cancer patients by enhancing knowledge relating to treatment.

2. OBJECTIVES

The primary objectives of this study are:

- Characterize the safety and tolerability of GS-5829 as a monotherapy in subjects with advanced solid tumors and lymphomas
- Determine the MTD or recommended dose for phase 2 study (RDP2) of GS-5829 as a monotherapy in subjects with advanced solid tumors and lymphomas
- Characterize the safety and tolerability of GS-5829 in combination with exemestane or fulvestrant in subjects with advanced estrogen receptor positive breast cancer
- Determine the MTD or RDP2 of GS-5829 in combination with exemestane or fulvestrant in subjects with advanced estrogen receptor positive breast cancer

The secondary objective of this study is:

- Evaluate the PK of GS-5829 alone in subjects with advanced solid tumors and lymphomas and in combination with exemestane or fulvestrant in subjects with advanced estrogen receptor positive breast cancer

CCI

[REDACTED]

[REDACTED]

[REDACTED]

[REDACTED]

[REDACTED]

[REDACTED]

[REDACTED]

[REDACTED]

3. STUDY DESIGN

3.1. Endpoints

The endpoints for this study are described in Section 8.

3.2. Study Design

This is an open-label, multicenter, sequential dose-escalation study to evaluate the safety, tolerability, PK, and PD of GS-5829 as a single agent in subjects with advanced solid tumors and lymphomas and in combination with exemestane or fulvestrant in subjects with advanced estrogen receptor positive breast cancer.

Group 1: Single agent GS-5829 in solid tumors and lymphomas

Cohorts of subjects with advanced solid tumors and lymphomas who have failed or are intolerant to standard therapy or for whom no standard therapy exists will be sequentially enrolled at progressively higher dose levels to receive oral GS-5829 as monotherapy once daily (QD). The starting dose will be 0.6 mg. Each dose level will enroll 1 subject until a \geq Grade 2 treatment-related toxicity is observed within the initial dosing period (Study Day 1 through C1D28 for all cohorts). At Dose Level 5 or if a \geq Grade 2 treatment-related toxicity is observed (whichever occurs first), the dose level will be expanded to 3 subjects. (Note: subjects enrolled with a Grade 2 hemoglobin [Hb] must have Hb worsen by at least 1 grade from baseline to be considered for expansion of the cohort to 3 subjects). Once a dosing level has been expanded to 3 subjects, a standard 3+3 study design will begin and, dose escalation [3+3] will be performed with cohort sizes of 3 to 6 subjects. Subjects in the first 3 cohorts will receive a single dose and then approximately 7 days later, initiate dosing once daily. Subjects will return to the clinic for frequent evaluation and monitoring as per [Appendix 2](#).

The doses for each candidate dose level in Group 1 are shown in [Table 3-1](#).

Table 3-1. Group 1: Single Agent GS-5829

Dose Level	GS-5829*
1	0.6 mg
2	1.4 mg
3	2 mg
4	3 mg
5	4 mg
6	6 mg
7	9 mg
8	12 mg

* Dose levels may be modified based on emerging safety and PK results.

If a DLT occurs within the 28 day DLT period at any dose level, this level will be expanded to enroll 3 additional subjects.

The safety and tolerability of each dose level will be assessed by a safety review team (SRT) after all subjects in the cohort have been followed for at least 28 days after the first dose of GS-5829. If no DLTs occur in up to 3 subjects or < 2 DLTs occur in up to 6 subjects on any Dose Level after 28 days on treatment, the next Dose Level will open. Each subsequent Dose Level will open if the Dose Level preceding has no DLTs in 3 subjects or < 2 DLTs in up to 6 subjects.

The SRT will consist of at least one investigator and the following:
Gilead Sciences, Inc. (Gilead) study team members: the medical monitor, representatives from Drug Safety and Public Health (DSPH), Clinical Operations, and Biostatistics. Others may be invited to participate as members of the SRT if additional expertise is desired. The medical monitor serves as the chair of the SRT.

Prior to initiating enrollment for Dose Level 4 in Group 1, an analysis of all available safety, PK, and PD data from previous cohorts will be reviewed.

If a subject is enrolled in a dose level but does not complete the PK or PD analysis, they may continue on study but an additional subject may be enrolled at that dose level.

The MTD is the highest dose level with a subject incidence of ≤ 1 DLT during the first 28 days of study drug dosing of 6 subjects. A minimum of 6 subjects need to be treated at a dose level before this dose level can be deemed as the MTD.

Group 2: Combination therapy of GS-5829 with exemestane or fulvestrant in patients with advanced stage estrogen receptor positive breast cancer

Cohorts of subjects with advanced estrogen receptor positive breast cancer for whom no standard curative therapy exists and who are candidates for exemestane or fulvestrant will be sequentially enrolled at progressively higher dose levels of oral GS-5829 in combination with full standard doses of exemestane or fulvestrant. The starting dose of GS-5829 will be 2.0 mg QD, which is a dose level that has been demonstrated to be safe and tolerable (no Grade 2 or higher drug related toxicity) in patients with solid tumors and prostate cancer. Dose escalation will continue with cohort sizes of 3-6 subjects in parallel arms: Group 2A will initiate with 2.0 mg of GS-5829 orally once daily on Cycle 1 Day 1 combined with 25 mg of exemestane once daily beginning on Cycle 1 Day 1. The subject may initiate exemestane anytime prior to, or on, Cycle 1 Day 1. Group 2B will initiate with 2.0 mg of GS-5829 orally once daily on Cycle 1 Day 1 with 500 mg fulvestrant administered intramuscularly (Cycle 1 Day 1 and then every 28 days (+/- 3 days)). If Cycle 1 Day 1 is the subject's first dose of fulvestrant, a one-time additional dose of fulvestrant should be administered on Cycle 1 Day 15).

The doses for each candidate dose level in group 2 are shown in [Table 3-2](#).

Table 3-2. Group 2: Combination of GS-5829 in Breast Cancer

Dose Level	GS-5829*	Group 2A Exemestane	Group 2B Fulvestrant
1	2 mg	25 mg orally once daily	500 mg intramuscularly day 1, 29 and then every 28 days**
2	3 mg		
3	4 mg		
4	6 mg		
5	9 mg		
6	12 mg		

* Dose Levels may be modified based on emerging safety and PK results.

** Subjects initiating fulvestrant on this study should receive a single additional dose of fulvestrant on Cycle 1 Day 15.

Group 2A and Group 2B will dose escalate independent of each other. In both Group 2A and Group 2B, each cohort will consist of 3 newly enrolled subjects who will be treated at the specified dose level. After all subjects in each cohort have been followed for at least 28 days after the first dose of GS-5829, a dose-DLT model (Bayesian logistic regression model) utilizing all available GS-5829 safety data will be built and will provide estimates of DLT rates at all dose levels. The dose-DLT model recommended dose for the next cohort will be the one having the highest chance that the DLT rate will fall in the target interval [16%, 33%) and a probability of <25% that the DLT rate exceeds 33%.

Group 3 Lymphoma expansion:

In addition to the minimum 6 subjects in Group 1 with solid tumors or lymphomas who will be enrolled to confirm the MTD, an additional minimum of 6 subjects with aggressive NHL (DLBCL or PTCL) may be enrolled at a dose no higher than the MTD and complete a 28 day safety period. If ≤ 1 of these 6 subjects reports a DLT within this 28 day safety period, then up to an additional 34 subjects may be enrolled to evaluate the efficacy and tolerability of GS-5829 in lymphoma (a maximum total of 40 subjects with lymphoma enrolled). A minimum of 20 DLBCL and 5 PTCL subjects will be enrolled into this group. If ≥ 2 of 6 subjects report a DLT, then an additional 6 subjects will be enrolled at a lower dose level, or at an alternative dosing schedule, which decreases the total amount of GS-5829 administered over a 28-day period to at least 25% less than the previous cohort (eg 14 days on and 7 days off).

The final dose escalation decisions will be made by the SRT, following a review of the model recommendation and all relevant data available including safety information, PK, CCI clinical data from evaluable patients.

Table 3-3. Group 3: Single agent expansion in aggressive lymphomas

Dose Level	GS-5829*	# of subjects enrolled initially	Total number of subjects
1	≤ MTD determined by Group 1	6 subjects	If no DLT in first 6 subjects expand to maximum total of 40 (approx. 34 additional subjects)
-1	is ≥25% less total GS-5829 administered over a 28 day period	6 subjects	If no DLT in 6 subjects at this dose level, then expand to maximum total of all Group 3 subjects of 40 (approx. 28 additional subjects)

Sites in France will be limited to Group 3 enrollment only.

Dose escalation in Group 1 will continue until identification of the MTD, or a suitable lower recommended dose, for Phase II studies. At least 6 subjects should be treated and evaluated at the GS-5829 dose level recommended for Phase II studies.

A DLT in Group 1 or 2 is a toxicity defined below considered possibly related to GS-5829 occurring during the DLT assessment window (Study Day 1 through C1D28) in each cohort.

- Grade ≥ 4 neutropenia (absolute neutrophil count [ANC] < 500/mm³)
- Grade ≥ 3 neutropenia (ANC < 1000/mm³) with fever (a single temperature of > 38.3°C or a sustained temperature of ≥ 38°C for more than one hour)
- Grade ≥ 3 thrombocytopenia
- Grade ≥ 2 bleeding (e.g. gastrointestinal, respiratory, epistaxis, purpura)
- Grade ≥ 3 or higher non-hematologic toxicity, except:
 - Grade 3 nausea or emesis with maximum duration of 48 hours on adequate medical therapy
 - Grade 3 diarrhea which persists for < 72 hours in the absence of maximal medical therapy
- Grade ≥ 2 non-hematologic treatment-emergent adverse event (TEAE) that in the opinion of the investigator is of potential clinical significance such that further dose escalation would expose subjects to unacceptable risk
- Treatment interruption of ≥ 7 days due to unresolved toxicity
- For certain toxicities such as laboratory assessments without a clear clinical correlate, a discussion between the Investigator and Medical Monitor may take place to determine if

this AE should be assessed as a DLT necessitating dose reduction. However, any Grade 3 or Grade 4 elevation in AST or ALT associated with a Grade 2 elevation in bilirubin that is at least possibly related to study drug will be considered a DLT.

Group 3: For the first 6 subjects enrolled in the aggressive lymphoma group (Group 3), a modification of the DLT assessment for hematologic toxicity will be:

- Grade ≥ 4 neutropenia (absolute neutrophil count [ANC] $< 500/\text{mm}^3$) which persist for > 3 days upon interruption of GS-5829 (administration of growth factors not allowed concurrently, but allowed during GS-5829 interruption)
- Grade ≥ 4 thrombocytopenia ($< 25,000/\text{mm}^3$)
- Grade ≥ 3 thrombocytopenia ($< 50,000/\text{mm}^3$ to $25,000/\text{mm}^3$ which persists for > 7 days upon interruption of GS-5829

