Group 2A and Group 2B will dose escalate independent of each other. In both Groups 2A and Group 2B, each cohort will consist of 3 newly enrolled subjects who will be treated at the specified dose level. After all subjects in each cohort have been followed for at least 28 days after the first dose of GS-5829, a dose-DLT model (Bayesian logistic regression model) utilizing all available GS-5829 safety data will be built, and will provide estimates of DLT rates at all dose levels.

The dose-DLT model recommended dose for the next cohort will be the one having the highest probability that the DLT rate will fall in the target interval (16%, 33%), and a probability of < 25% that the DLT rate exceeds 33%.

Group 3 Lymphoma expansion:

In addition to the minimum 6 subjects in Group 1 with solid tumors or lymphomas who will be enrolled to confirm the MTD, an additional minimum of 6 subjects with aggressive NHL (DLBCL, or PTCL) may be enrolled at a dose no higher than the MTD and complete a 28 day safety period. If ≤ 1 of these 6 subjects reports a DLT within this 28 day safety period, then up to an additional 34 subjects may be enrolled to evaluate the efficacy and tolerability of GS-5829 in lymphoma (a maximum total of 40 subjects with lymphoma enrolled). A minimum of 20 DLBCL and 5 PTCL subjects will be enrolled into this group. If ≥ 2 of 6 subjects report a DLT, then an additional 6 subjects will be enrolled at a lower dose level, or at an alternative dosing schedule, which decreases the total amount of GS-5829 administered over a 28-day period to at least 25% less than the previous cohort (eg 14 days on and 7 days off).

The final dose escalation decisions will be made by the SRT, following a review of the model recommendation and all relevant data available including safety information, PK, biomarkers, clinical data from evaluable patients.

Group 3: Single agent expansion in aggressive lymphomas

Dose Level	GS-5829*	# of subjects enrolled initially	Total number of subjects
1	\leq MTD determined by Group 1	6 subjects	If no DLT in first 6 subjects expand to maximum total of 40 (approx 34 additional subjects)
-1	is $\geq 25\%$ less total GS-5829 administered over a 28 day period	6 subjects	If no DLT in 6 subjects at this dose level, then expand to maximum total of all Group 3 subjects of 40 (approx 28 additional subjects)

Sites in France will be limited to Group 3 enrollment only.

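### Group 3 expansion: both dose level 1 table cells require no DLT in the first 6 subjects, while the text allows up to 1 of 6, and no document says which governs

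*Protocol*

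**What the plan says.** The Group 3 text is the same in Protocol Section 3.2 and in the synopsis. It opens expansion "If ≤ 1 of these 6 subjects reports a DLT within this 28 day safety period", and "then up to an additional 34 subjects may be enrolled to evaluate the efficacy and tolerability of GS-5829 in lymphoma". It then gives the opposite branch: "If ≥ 2 of 6 subjects report a DLT, then an additional 6 subjects will be enrolled at a lower dose level", or on an alternative schedule that cuts the 28-day total dose by at least a quarter.

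The tables that accompany this text give another condition. Table 3-3, dose level 1: "If no DLT in first 6 subjects expand to maximum total of 40 (approx. 34 additional subjects". Synopsis table, dose level 1: "If no DLT in first 6 subjects expand to maximum total of 40 (approx 34 additional subjects".

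The dose level -1 row of both tables also conditions expansion on no DLT in its 6 subjects. The text gives no expansion threshold for that second cohort.

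Two neighbouring rules in Section 3.2 bear on which version was meant. The MTD definition reads "The MTD is the highest dose level with a subject incidence of ≤ 1 DLT during the first 28 days" and is based on 6 subjects. The Group 1 rule opens the next level at fewer than 2 DLTs in up to 6. After the Group 3 text comes the statement "The final dose escalation decisions will be made by the SRT", with no threshold attached. SAP Section 1.2 describes only Groups 1 and 2.

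**The concern.** One decision, whether to open enrolment of up to 34 more lymphoma subjects at a dose, has two thresholds in the current protocol. A site or safety review team working from the table would take zero DLTs as the criterion; one working from the text would take at most one. The conflict appears in both the synopsis and the body, and the condition is written out in words in the cells, so it is neither a lost symbol nor a redaction. French sites may enrol only in Group 3, so this is the one cohort-level expansion rule that applies to them.

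At stake is whether the decision follows a rule fixed in advance. With exactly 1 DLT in 6, the choice could be justified either way after the event, from a different part of the same protocol.

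**Working it through.** **1. The plan's own figure.** The Group 3 maximum is 40. At level 1, 6 + 34 = 40. By way of level -1, 6 + 6 + 28 = 40. Both reproduce, and neither depends on the DLT threshold.

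**2. The two rules by outcome in the first 6 subjects.**

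| DLTs in 6 | Text | Level 1 table cell |
|---|---|---|
| 0 | expansion permitted | expand |
| 1 | expansion permitted | condition not met; no action stated |
| 2 to 6 | lower dose or schedule | condition not met |

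The text assigns an action to every outcome. The rules part only at exactly 1.

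**3. How often that outcome would arise.** The documents give no DLT rate for Group 3, so the true rate p is an assumption, taken from 2% to 33%. The 16% and 33% values are the edges of the Group 2 model's target interval, used only as reference points. The comparison takes the table cell to mean that expansion opens *only if* there is no DLT.

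With the number of DLTs distributed as Binomial(6, p):

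- Table rule opens expansion: P(0) = (1 − p)^6
- Text rule permits expansion: P(0) + P(1)
- Difference: P(1) = 6p(1 − p)^5

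Example at p = 0.10: P(0) = 0.9^6 = 0.531; P(1) = 6 × 0.10 × 0.9^5 = 0.354; sum = 0.886.

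| Assumed p | P(0), table | P(0) + P(1), text | P(1), rules differ |
|---|---|---|---|
| 2% | 0.886 | 0.994 | 0.108 |
| 5% | 0.735 | 0.967 | 0.232 |
| 10% | 0.531 | 0.886 | 0.354 |
| 16% | 0.351 | 0.753 | 0.401 |
| 33% | 0.090 | 0.358 | 0.267 |

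P(1) is largest at p = 1/6, where it equals (5/6)^5 = 0.402. Over the assumed range it therefore runs from 11% to 40%.

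**4. Which version is more likely intended.** The rule of at most 1 in 6 appears identically in two text locations, is paired with its exact complement (2 or more in 6), and agrees with the MTD definition and the Group 1 rule. The zero-DLT version agrees only with itself across the two tables and leaves 1 of 6 without an instruction. This points to the cells as the error but does not prove it.

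**The case against.** The strongest reply is that the cell says what happens with no DLT and does not say *only if*. On that reading it forbids nothing at 1 of 6, the text is the sole express instruction there, and nothing is left to resolve. This has some force: the text does largely settle the matter, and the table-versus-text probabilities depend on the stricter reading. But a condition in a decision table is normally taken as the criterion, and even on the lenient reading the table omits an outcome that the text covers.

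A second reply is that little follows from the mismatch. This stands. The text only permits expansion, so declining at 1 of 6 breaches neither version; the dose cannot exceed the Group 1 MTD; the individual hold and reduction rules in Section 6.7.1 continue to apply; and SAP Section 7.1.7.1 plans only a listing of DLTs. SAP Section 1.3 reports 33 subjects enrolled in the whole study, so the Group 3 maximum of 40 was not reached. That figure does not show whether the six-subject decision was ever reached, because Group 3 enrolment is not given.

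A reader might also infer that the level -1 cells are wrong in the same way. The documents do not support that. The text sets no threshold for that cohort, so nothing there contradicts the cell. The words "which decreases the total amount of GS-5829 administered over a 28-day period to at least 25% less than the previous cohort" fix the size of the dose reduction; reading them as a repeat of the trigger is strained. After 2 or more DLTs in 6 at level 1, a stricter gate at the next step could be deliberate.

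**Conclusion.** The inconsistency is real and confined to the two dose level 1 cells. Text and tables differ only at exactly 1 DLT in 6, an outcome with probability 11% to 40% over assumed true DLT rates of 2% to 33%, if the cell is taken as a necessary condition. These rates are illustrative; Group 3 also uses modified hematologic DLT criteria for its first 6 subjects, so rates from the other groups would not carry over directly.

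The table cells are the likely error. To call them a wrong threshold outright would go too far, since the two tables agree with each other and no document gives precedence to text or table. Nor do the documents show that any subject was enrolled under the wrong rule. The consequence is limited, but a rule that controls up to 34 enrolments should have one threshold, and the correction is simple.

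**What to change.** - **Level 1.** In Table 3-3 and the synopsis table, change the dose level 1 condition to at most 1 DLT in the first 6 subjects, matching the text. If zero was intended, change the text in both places instead and state what happens at 1 of 6.
- **Level -1.** Ask the sponsor to confirm whether 0 of 6 is intended, and to state the action if that condition is not met. Do not relax it by default: moving it to at most 1 of 6 would change a safety rule, which is more than a wording correction.

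The preferred level 1 correction is wording only, in two cells. The maximum of 40, the study procedures and the analyses stay as they are.
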